Key Secondary: Proportion of patients with ≥ 1 COVID-19 related medically attended visit	Patients with ≥ 1 COVID-19 related medically attended visit through to study end (including early termination visits)	Treatment-policy strategy approach will be taken. Patients are followed, assessed and analyzed irrespective of their completion of the planned course of the study treatment and irrespective of rescue and concomitant therapy (contd.)	Composite strategy where patient considered as having the event if they die (contd.)	Difference in proportion of patients between treatments (contd.)	The outcome measure up to point of study withdrawal will be used (contd.)
Secondary: Proportion of patients with any post treatment infection	Patients with any post treatment infection through to study end (including early termination visits)		Not an intercurrent event as it is the outcome measure		
Key Secondary: Frequency (Proportion) of COVID-19 related complications (including hospitalizations and deaths)	Patients with a medically confirmed COVID-19 related complication through to study end (including early termination visits)				
Key Secondary: Proportion of patients with all-cause mortality	Patients with all-cause mortality through to study end (including early termination visits)				

Table 2 Estimands (cont.)

Endpoint	Variable or Outcome Measurement	Intercurrent Events		Population-Level Summary for the Variable	Handling of Missing Data
		Treatment Withdrawal/Rescue/Concomitant Medications	Death		
Secondary (Virology): Change from baseline in amount of SARS-CoV-2 virus RNA	Amount of SARS-CoV-2 virus RNA, as measured by RT-qPCR at Day 3, Day 5, Day 7 and Day 14	Treatment-policy strategy approach will be taken. Patients are followed, assessed and analyzed irrespective of their completion of the planned course of the study treatment and irrespective of rescue and concomitant therapy.	While on treatment approach where the outcome measure up to point of intercurrent event will be used	Difference in mean change from baseline between treatments	The outcome measure up to point of study withdrawal will be used
Secondary (Virology): AUC in amount of SARS-CoV-2 virus RNA	Amount of SARS-CoV-2 virus RNA, as measured by RT-qPCR to Day 14			AUC for each treatment	

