5.1 GENERAL CONSIDERATION

All statistical tests will be performed at a 0.025 significance level using two-sided tests, unless otherwise noted. As specified in Section 2.2, key secondary endpoints for which the multiplicity-adjusted p-value is greater than 0.025 will not be considered statistically significant. These endpoints and all endpoints not under multiplicity control will be considered to provide supportive information.

Statistical tests will use stratification factors according to IxRS unless there is considerable imbalance in IxRS and electronic Case Report Form (eCRF) stratum classification. Stratification factors may need to be removed or have their levels combined so that low or zero counts in one stratum do not invalidate relevant statistical tests.

Unless otherwise specified, continuous variables will be summarized by using the number of non-missing observations, arithmetic mean, standard deviation (SD), median, minimum, and maximum values as summary statistics; categorical variables will be summarized by using the frequency count and the percentage of subjects in each category as summary statistics. Descriptive summaries will be tabulated by treatment group.

All efficacy and virology analyses will be performed on the efficacy-evaluable set, all patient disposition and study conduct analyses will be performed on the All Patients set, and all safety analyses will be performed on the safety-evaluable set, unless otherwise specified.

Missing data due to study withdrawal or lost to follow up will be handled as described in Table 2. Any other missing data will not be imputed unless otherwise specified in the specific section describing an endpoint.

Time to event secondary efficacy and virology endpoints will use the same statistical methods as used for the primary endpoint as described in Section 5.3.2, and will be measured in days unless otherwise stated.

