For time to event efficacy endpoints, once the first instance of the criteria has been met at an assessment, assessments with endpoint data present prior to the assessment that demonstrates the criteria is maintained for the required duration (either ≥ 21.5 hours or ≥ 43 hours as appropriate), must also meet the criteria to meet the endpoint i.e., subsequent assessments after a patient first meets the criteria but prior to the assessment showing maintenance of that criteria for 21.5 hours (or 43 hours if appropriate) must also meet the criteria if there is non-missing data at these assessments.

In addition, for time to event efficacy endpoints, once the endpoint has been met, subsequent data for a patient that does not meet the efficacy criteria will not result in a

null endpoint. Due to this, these endpoints can also be thought of as the time to first instance of a maintained defined criteria (such as alleviation) where maintained here refers to the required duration.

Secondary efficacy and virology endpoints that evaluate proportion of patients will be analyzed using a Cochran-Mantel-Haenszel test adjusted by the stratification factors for region (North America, Europe, ROW) and high-risk factor (yes, no), unless stated otherwise. The proportion in each treatment arm together with the difference in proportions, odds ratio and accompanying 97.5% CIs will be presented along with the p-value.

Continuous secondary virology endpoints, such as change from baseline endpoints, will be analyzed using an analysis of covariance (ANCOVA) model with region (North America, Europe, and ROW), high-risk factor (yes, no) as stratification variables, and the baseline value of the studied measure as a covariate. The least squares mean (LSM) change and its standard error (SE) of means in each group, the difference between two groups in least squares mean (LSM change), SE, and 97.5% CI, and p-values will be presented. Additionally, descriptive summaries for the change from baseline will also be presented by treatment group.

Area under the concentration curve (AUC) for secondary and exploratory endpoints will be analyzed using the van Elteren test where AUC is calculated using the trapezoidal method. AUC of change from time 0 (t_0) to time K (t_k) is given by the formula:

$$\sum_{k=1}^K \frac{(y_k + y_{k-1})(t_k - t_{k-1})}{2},$$

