where t_k (hours) represents the date of the k^{th} virus RNA (reverse-transcriptase polymerase chain reaction [RT-PCR]) assessment ($k = 0, \dots, K$) and y_k represents the \log_{10} value of the k^{th} virus RNA (RT-PCR) assessment. 24-hours of time will be converted into one day.

Descriptive summary statistics of the AUC will be presented for each treatment group along with the p-value from the van Elteren test.

All secondary virology endpoints will be evaluated on the nasopharyngeal swab samples. Additional descriptive analyses for saliva and serum samples will be performed on an exploratory basis for the secondary virology endpoints, as required.

The qualitative result of the SARS-CoV-2 reverse-transcriptase polymerase chain reaction (RT-PCR) test is determined using cycle threshold (Ct) values. If the qualitative result is positive, then an associated quantitative result is also provided. The quantitative result is either numerical or below the limit of quantification (BLQ). The limit of quantification (LOQ) for the virus RNA is 120 copies/ml. If the virus RNA sample has a

positive qualitative result, but a quantitative result BLQ, virus RNA will be imputed as LOQ – 1 (119 copies/mL). Negative qualitative samples will be imputed as LOQ/2 (60 copies/ml) before being transformed to the log10 scale.

Baseline is defined as the last available assessment prior to first dose of study treatment. For efficacy analyses, if there is no such assessment available then baseline can be up to 4 hours post first dose, with the earliest assessment used as baseline in the case of multiple assessments within this time.

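### The viral RNA AUC scores a series that ends before Day 14 as better clearance, so unequal early losses between arms bias this supportive comparison

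*SAP*

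**What the plan says.** In SAP Table 2 (section 1.1) the AUC variable is "Amount of SARS-CoV-2 virus RNA, as measured by RT-qPCR to Day 14". The row appears to share its handling cells with the change-from-baseline row above it. For withdrawal or loss to follow-up the rule is "The outcome measure up to point of study withdrawal will be used". For death it is "While on treatment approach where the outcome measure up to point of intercurrent event will be used".

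SAP 5.1 says that AUC endpoints "will be analyzed using the van Elteren test where AUC is calculated using the trapezoidal method". Each y_k in the sum is the log10 "value of the k^{th} virus RNA (RT-PCR) assessment". The sum runs to the patient's own last assessment and is not divided by its length. Negative swabs "will be imputed as LOQ/2 (60 copies/ml) before being transformed to the log10 scale". On other gaps, SAP 5.1 says "Any other missing data will not be imputed unless otherwise specified". SAP 5.4.3.3 only refers back to 5.1. The multiple imputation in SAP 5.5.1 covers three clinical proportions, not the AUC, and no sensitivity analysis is given for the AUC.

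Three provisions limit the problem:

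- Patients who stop only the drug stay on the visit schedule (Protocol Appendix 1, footnote e).
- Patients who leave the study by Day 14 are due an early termination visit 7 (±2) days after their final dose (Protocol 4.6.2). Appendix 1 schedules a nasopharyngeal swab at that visit.
- The AUC is listed as supportive (SAP 5.4.3), and SAP 5.1 states that "all endpoints not under multiplicity control will be considered to provide supportive information".

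**The concern.** An AUC to Day 14 is comparable between patients only if each series covers the same span. Here the integrand can never reach zero, so each further day of follow-up adds area, even in a patient who has already cleared the virus. Withdrawal, loss to follow-up and death before Day 14 all shorten the span and lower the score, and a low score counts as good antiviral activity.

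If early losses differ between arms, the van Elteren p-value partly measures length of follow-up and favours the arm that loses more patients. A death before Day 14 likewise improves that patient's rank.

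**Working it through.** **Inputs from the documents.** Swabs on Days 1, 3, 5, 7 and 14 (Protocol Appendix 1); negative swab = 60 copies/mL; two-sided 0.025; 2:1 allocation of 1248 evaluable patients, giving 832 and 416. The plan has no power, effect or loss figure for the AUC. Its only sample-size figure is for the primary endpoint, and it reproduces: (2.2414 + 1.2816)² / [(2/3)(1/3)(ln 1.25)²] = 1122 events.

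**Step 1: the floor.** log10(60) = 1.778. Losing Days 7 to 14 removes at least 7 × 1.778 = 12.4 log10 × days.

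**Step 2: a patient negative at every swab.** AUC = 1.778 × days covered. To Day 14: 1.778 × 13 = 23.1. Ending at Day 3, 5 or 7: 1.778 × 2 = 3.6, × 4 = 7.1, × 6 = 10.7.

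**Step 3: ranks can invert.** Take an assumed slow clearer at 6.5, 6, 5.5, 5 and 4 on the five days.

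- To Day 7: 12.5 + 11.5 + 10.5 = 34.5. The last interval adds (5 + 4) × 7/2 = 31.5, so the complete AUC is 66.0.
- An assumed fast clearer with complete data (6.5, 4.5, 3, negative, negative) scores 11 + 7.5 + 4.78 + 12.45 = 35.7.
- The slow clearer lost after Day 7 (34.5) therefore ranks as the better result.

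**Step 4: only lost ends matter.** Under the Step 5 curves, mean AUC is 52.2 for complete series and 12.1, 22.4 or 31.1 when the series ends at Day 3, 5 or 7. Missing Day 7 alone gives 53.4, and missing Days 5 and 7 gives 54.8, because the trapezoid bridges interior gaps.

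**Step 5: effect on the test when there is no treatment effect.** Assumptions:

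- Baseline 6.5 (SD 1.5) log10, decline 0.45 (SD 0.10) per day, residual SD 0.5, floor 1.778.
- Six region-by-risk strata with assumed shares (regions 0.3/0.4/0.3, risk 0.5).
- Leavers' last scheduled swab spread evenly over Days 3, 5 and 7; early termination swab on Day 10 to 13.
- 5,000 trials per row, Monte Carlo SE 0.2 to 0.5 points.

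Rejection rate (%) at nominal 2.5%, by share of leavers who give an early termination swab:

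| Loss in the two arms | 0% | 50% | 80% |
|---|---|---|---|
| 5% v 5% | 2.4 | 3.0 | 2.7 |
| 2% v 1% | 3.1 | 2.6 | 2.6 |
| 3% v 2% | 2.8 | 2.6 | 2.5 |
| 4% v 3% | 3.0 | 2.7 | 2.7 |
| 5% v 3% | 4.1 | 3.5 | 2.9 |
| 6% v 3% | 7.4 | 4.0 | 3.3 |
| 8% v 4% | 11.4 | 5.4 | 3.9 |
| 10% v 5% | 18.0 | 7.8 | 4.5 |

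At 10% v 5% with no such swab, 17.98 of the 18.00 points favour the arm with more loss.

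A separate simulation with different curves (baseline 6.0, slope SD 0.15, 2,000 trials) gave 18.3% for the same case, or 12.0% if every loss came after Day 7. With the loss reversed to 5% active v 10% placebo it gave 16.0%, all against active.

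**Step 6: candidate remedies** (Step 5 curves, no early termination swab, 3,000 trials, 5 imputations). Rejection rate (%):

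| Loss pattern | As written | Complete series | Imputed | Divided by time |
|---|---|---|---|---|
| 6% v 3%, unrelated to RNA | 7.4 | 2.7 | 2.4 | 4.1 |
| 10% v 5%, unrelated to RNA | 17.4 | 1.7 | 1.8 | 6.9 |
| 6% v 3%, higher with high Day 3 RNA | 9.6 | 3.4 | 2.9 | 3.8 |
| 10% v 5%, higher with high Day 3 RNA | 24.4 | 3.5 | 2.6 | 7.0 |

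The excess from dividing by time runs in the opposite direction.

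**The case against.** The strongest reply concerns size. The 18.0% needs twice the loss in one arm and no early termination swabs, although one is scheduled. At 80% attendance even 10% v 5% gives 4.5%, and the documents do not suggest such an imbalance. SAP 5.2 tabulates discontinuation and visit disposition by arm, so a large imbalance would be visible. All of this stands, and it is why the point is only a cheap improvement. Seeing an imbalance does not correct the p-value, however, and the swab does not help with deaths, losses to follow-up or leavers who do not attend. Nor does it help a patient still in the study who misses Day 14.

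The simulated swab timing is approximate. A patient whose last dose is on Day 3 would be due at Day 8 to 12, not Day 10 to 13, so the attendance columns are slightly optimistic for early leavers.

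The SAP formula is introduced as an *AUC of change*. If change from baseline were integrated, the direction would flip: the slow clearer would score −18.5 complete and −4.5 to Day 7. The definition of y_k as the log10 value settles the reading used here, but the label needs correcting.

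Complete series perform almost as well as imputation, so imputation is a preference and not the only sound choice. The 1.7% and 1.8% entries are somewhat below nominal. Imputing to Day 14 for everyone would also impute RNA after death, so deaths need their own rule.

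**Conclusion.** The concern holds. Applied as written, the rule gives a lower AUC to any series that ends before Day 14, and this follows from the formula and the floor without further assumption. Reading the withdrawal and death rules as covering the AUC row rests on the table layout, which is the natural reading.

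The size of the bias depends on assumed loss rates, swab attendance and viral curves. It is negligible for equal losses or a 1-point difference. It is material only for larger imbalances with few early termination swabs: 7.4% at 6% v 3% and 18.0% at 10% v 5% with none.

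Change from baseline by day, proportion positive by day and time to cessation do not sum over follow-up and are not affected. Neither are the primary and key secondary tests.

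**What to change.** Amend SAP 5.1 and the AUC row of Table 2 before unblinding:

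- Compute the AUC over one fixed Day 1 to Day 14 window for every patient. State that early termination swabs enter at their actual dates. SAP 5.1 implies this by using assessment dates without time windows, but does not say it.
- Complete missing later swabs by multiple imputation from arm, baseline and earlier log10 RNA, with draws floored at log10(60). Combine the van Elteren statistic across imputations.
- Report complete series only as a sensitivity analysis.
- Do not divide by observed time, which reverses the bias.
- State how deaths before Day 14 enter the AUC, so that a death cannot improve a patient's rank.
- Correct the *AUC of change* label to match y_k as the log10 value.

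The cost is a few lines of text and modest programming, with no new data. The downside is that imputation assumes data missing at random and needs care with values at the floor.

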4.2.2 Blinding

Study site personnel and patients will be blinded to treatment assignment during the study. The Sponsor and its agents will also be blinded to treatment assignment, with the exception of individuals who require access to patient treatment assignments to fulfill their job roles during a clinical trial. These roles include the unblinding group responsible, clinical supply chain managers, sample handling staff, operational assay group personnel, IxRS service provider, and iDMC members.

While PK samples must be collected from patients assigned to the comparator arm to maintain the blinding of treatment assignment, PK results for these patients are generally not needed for the safe conduct or proper interpretation of the study data. Laboratories responsible for performing study drug PK will be unblinded to patient treatment assignments to identify appropriate samples for analysis. PK samples from patients assigned to the comparator arm will not be analyzed for study drug PK concentration except by request (e.g., to evaluate a possible error in dosing).

If unblinding is necessary for a medical emergency (e.g., in the case of a serious adverse event for which patient management might be affected by knowledge of treatment assignment), the investigator will be able to break the treatment code by contacting the IxRS. The treatment code should not be broken except in emergency situations. The investigator is not required to contact the Medical Monitor prior to breaking the treatment code. However, the investigator should contact the Medical Monitor to discuss emergency unblinding after the treatment code has been broken.

As per health authority reporting requirements, the Sponsor's Drug Safety representative will break the treatment code for all serious, unexpected suspected adverse reactions (see Section 5.7) that are considered by the investigator or Sponsor to be related to an investigational medicinal product (IMP; defined in Section 4.3). The patient may continue to receive treatment, and the investigator, patient, and Sponsor personnel, with

the exception of the Drug Safety representative and personnel who must have access to patient treatment assignments to fulfill their roles (as defined above), will remain blinded to treatment assignment.

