Appendix 1: Schedule of Activities

Assessments in parentheses (x) should be performed as needed.

- ^a For patients at participating sites who have provided written informed consent to participate in mobile nursing visits, select assessments or procedures may be performed by a trained nursing professional at the patient's home for visits after Day 1. For patients who have provided written informed consent, procedures may be performed by a physician at the patient's home at any visit.
- ^b All assessments (except sample collection) for these visits can be conducted remotely (e.g., via telephone or telemedicine), in clinic or at home.
- ^c End of study visit can either be in person, telephone call or telemedicine call.
- ^d *Optional exit interviews in a subset of patients to be conducted within 14 days after the Day 33 visit.*
- ^e Patients who complete study treatment or discontinue study drug prematurely should continue to complete assessments as indicated until the end of the study. Patients who discontinue from study participation will return to the clinic for an early termination visit 7 (± 2) days after their final dose of study drug. Patients who discontinue from the study after Day 14 will not be required to complete an early termination visit. COVID-19 Symptom Diary, PGIS, EQ-5D-5L and self-reported temperature assessments should be completed at the ET visit; one single entry will be assessed.
- ^f Informed consent must be documented before any study-specific screening procedure is performed.
- ^g At screening, symptom severity assessment and pre-existing symptom assessment to be done together to confirm patient eligibility.
- ^h Includes SpO₂, temperature, respiratory rate, pulse rate, and systolic and diastolic blood pressure while the patient is in a seated position.
- ⁱ Includes evaluation of the head, eyes, ears, nose, and throat, and the cardiovascular, dermatologic, musculoskeletal, respiratory, gastrointestinal, genitourinary (as clinically indicated), and neurologic systems.
- ^j Perform a limited, symptom-directed examination *or assessment* as clinically indicated.
- ^k For patients who have provided written informed consent, the Medically Attended Visit(s) assessment can be completed by a physician/trained nursing professional at the patient's home. This assessment can also be completed via telemedicine with a physician or at site. All details to be recorded in the eCRF at all visits. For details of the assessment see Section 4.5.6.3.

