	8 hours postdose (±30 min)	RO7496998 (AT-527) PK (plasma)
Day 7	Anytime ^c	RO7496998 (AT-527) PK (plasma)

PK=pharmacokinetic.

- ^a PK samples to be collected in adult and adolescent patients. Samples can be collected and processed in clinic/at site or at home (if patients consented to home visits).
- ^b Optional PK samples to be collected in adult patients only, and who have consented to PK intensive sampling. Samples to be collected and processed at site only.
- ^c The exact sampling time will be captured in relation to the time of last (10th) dose.

Appendix 3

Temperature

Do not reproduce or distribute. The Sponsor will provide sites with all instruments to be completed in this study.

Temperature:

Please take your temperature now.

What is your temperature right now? (Measure before taking fever medication):

_____ (Choose °C or °F)

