Secondary (PK): Plasma concentration of AT-511, AT-551, AT-229, and AT-273	Plasma concentration of AT-511, AT-551, AT-229, and AT-273	Treatment-policy strategy approach will be taken. Patients are followed, assessed and analyzed irrespective of their completion of the planned course of the study treatment and irrespective of rescue and concomitant therapy (contd.)	While on treatment approach where the outcome measure up to point of intercurrent event will be used (contd.)	Means for each treatment (contd.)	The outcome measure up to point of study withdrawal will be used (contd.)

AUC=area under the concentration–time curve; COVID-19=coronavirus disease 2019; NCI CTCAE=National Cancer Institute Common Terminology Criteria for Adverse Event; PK=pharmacokinetic; RT-qPCR=reverse-transcriptase quantitative polymerase chain reaction ; SARS-CoV-2=severe acute respiratory syndrome-corona virus-2; SpO₂=peripheral capillary oxygen saturation TTAS=time to alleviation of symptoms TTAIS=time to alleviation or improvement of symptoms.

Target Population: Adult and adolescent patients with mild or moderate COVID-19 defined through inclusion/exclusion criteria.

Treatment: Primary treatment effect comparison will be between the RO7496998 (AT-527) arm and the placebo arm regardless of other therapies.

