5.4.5 Supportive Secondary PK Endpoints

Samples taken for PK analysis will be processed to plasma and concentrations of AT-511 (free base form of AT-527) and its major metabolites AT-551, AT-229, and AT-273, will be quantified by a validated liquid chromatography-tandem mass spectrometry method.

Descriptive summary statistics for PK concentration data will be provided by visit/sampling time point. Summary statistics will also include geometric mean and coefficient of variation (CV; arithmetic and geometric). Concentrations below lower limit of quantification (LLOQ) will be treated as zero in summary statistics and for PK

parameter calculations. Individual and mean plasma concentration versus time data for AT-511, AT-551, AT-229, and AT-273 will be summarized and plotted.

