5.7.3 Pharmacokinetic Analyses

The following pharmacokinetic parameters will be determined on Day 1: maximum concentration (C_{max}), time to maximum concentration (T_{max}) after the first dose from the plasma concentration-time data. At steady state on Day 5 the following PK parameters will be determined: $C_{max,ss}$, $T_{max,ss}$, and $C_{trough,ss}$. All PK analysis will be performed using the actual recorded sampling times for AT-511, AT-551, AT-229, and AT-273.

Descriptive summary statistics for PK parameters will include mean (arithmetic and geometric), SD, CV (arithmetic and geometric), median, minimum, and maximum.

An exception to this is T_{max} where median, minimum, and maximum will be presented.

Inter-patient variability and drug accumulation will be evaluated.

Nonlinear mixed effects (NLME) modeling will be used to analyze the dose-concentration-time data of AT-511 and AT-273 in plasma. Population and individual PK parameters (e.g., apparent clearance [CL/F] and apparent steady-state volume of distribution [V_{ss}/F]) will be estimated and the influence of various covariates (e.g., age, sex, and weight) on these parameters will be investigated. The data collected during this study may be pooled with data collected in other clinical studies (previous Phase I and/or Phase II study in healthy volunteers and patients infected with hepatitis C virus [HCV], COVID-19) as appropriate, to build the population PK model. Secondary PK parameters may be derived from the individual post-hoc predictions. NLME modeling results will be reported in a standalone document distinct from the clinical study report.

Additional PK analyses may be conducted as appropriate. The PK data and parameters derived from these analyses may be used for exploratory graphical analyses of the PD data and parameters.

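### The PK row of SAP Table 2 applies treatment policy to stopping study drug, which conflicts with Day 5 descriptive PK summaries labelled as steady state

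*SAP*

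**What the plan says.** SAP Table 2 gives the PK endpoint (plasma AT-511, AT-551, AT-229 and AT-273) the same strategy for treatment withdrawal, rescue and concomitant medication as the efficacy endpoints: "Patients are followed, assessed and analyzed irrespective of their completion of the planned course of the study treatment". A while-on-treatment strategy does appear in that row, but only in the Death column. The population-level summary is a mean for each treatment.

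The other relevant text is:

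- SAP 5.7.3, introducing Cmax,ss, Tmax,ss and Ctrough,ss: "At steady state on Day 5 the following PK parameters will be determined".
- SAP 5.4.5, which summarises concentrations by visit and sampling time: "Concentrations below lower limit of quantification (LLOQ) will be treated as zero in summary statistics". The same zero rule applies to parameter calculations.
- SAP 4: the PK-evaluable set requires one dose and enough data to estimate key parameters. It is defined per patient, not per sample.
- Protocol Appendix 1, footnote e: patients who "discontinue study drug prematurely should continue to complete assessments as indicated until the end of the study". Protocol 4.6.1 says the same in substance.
- Protocol Appendix 2: Day 5 samples are timed from that day's morning dose. The Day 7 sample may be taken at any time, and its footnote reads: "The exact sampling time will be captured in relation to the time of last (10th) dose".
- Protocol 4.2.2: "PK samples from patients assigned to the comparator arm will not be analyzed for study drug PK concentration", except by request, for example to look into a possible dosing error.

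**The concern.** The secondary PK objective is to characterise the plasma profile of AT-511 and its main metabolites. Treatment policy suits an efficacy comparison, where the effect of assigning the drug is of interest whether or not the course is finished. Applied to concentrations, it mixes exposure on the regimen with how many patients were still taking it. A patient who has stopped is not at steady state, so the estimand row and the steady-state label cannot both hold for that patient's Day 5 sample.

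Trough is where this matters most. Protocol 3.3.1 supports the regimen by comparing a predicted AT-9010 lung trough of about 0.9 µM with an EC90 of 0.5 µM, and plasma AT-273 is the stated surrogate for AT-9010. Off-drug samples would lower the reported trough and inflate the inter-patient variability that SAP 5.7.3 plans to evaluate.

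**Working it through.** The documents state no PK sample size, precision target or discontinuation rate, so there is no planned figure to reproduce. The check traces the rule through the text and then sizes its effect over an assumed range.

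**1. Does anything remove an off-drug Day 5 sample?** A patient who stops on, say, Day 3 stays on the schedule, which includes the Day 5 PK draw. The Day 1 pre-dose and 1-hour samples might be enough to make that patient PK-evaluable. Once in the set, no sample-level screen applies in SAP 5.4.5 or 5.7.3. Table 2 says to analyse regardless of completion. Its missing-data column covers withdrawal from the study, not stopping drug.

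**2. Arithmetic and geometric means.** Let d be the share of sampled AT-527 patients off drug on Day 5 and r their concentration as a fraction of the on-drug mean (arithmetic or geometric, as the case may be). Both are assumptions. Relative to the on-drug value:

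- arithmetic mean ratio = 1 − d(1 − r)
- geometric mean ratio = r^d

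| d | Arithmetic, r = 0 | Arithmetic, r = 0.5 | Geometric, r = 0.25 | Geometric, r = 0.5 |
|---|---|---|---|---|
| 1% | 0.990 | 0.995 | 0.986 | 0.993 |
| 2% | 0.980 | 0.990 | 0.973 | 0.986 |
| 5% | 0.950 | 0.975 | 0.933 | 0.966 |
| 10% | 0.900 | 0.950 | 0.871 | 0.933 |

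The arithmetic loss cannot exceed d. At r = 0 the geometric mean is zero or undefined, and neither document says how zeros enter it.

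**3. Arithmetic CV, r = 0.** CV′ = √[(1 + CV²)/(1 − d) − 1]. A true CV of 40% becomes 41%, 43%, 47% and 54% at d = 1%, 2%, 5% and 10%. A true CV of 60% becomes 61%, 62%, 66% and 71%.

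**4. Median.** If the off-drug values all lie at the bottom, the median of the mixture is the (0.5 − d)/(1 − d) quantile of the on-drug distribution: 0.49/0.99, the 49.5th percentile, at d = 1%, and 0.40/0.90, the 44.4th, at d = 10%.

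**5. How many patients?**

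- Whole AT-527 arm: 1386 × 2/3 = 924, so 9.2 stoppers are expected at d = 1% and 92.4 at d = 10%.
- Optional intensive cohort: 65 × 2/3 ≈ 43 on AT-527, if the 2:1 split holds there. One zero lowers that mean by 1/43 = 2.3%. The chance of at least one stopper, 1 − (1 − d)^43, is 35% at d = 1% and 89% at d = 5%.

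**6. Day 7.** Under Protocol 4.3.2.1 the tenth dose falls on the evening of Day 5 or the morning of Day 6. With assumed clock times (first dose at 08:00 or 20:00, Day 7 visit between 08:00 and 18:00), nine 12-hour intervals put the tenth dose at 20:00 on Day 5 or 08:00 on Day 6. The Day 7 sample is then 36 to 46 hours or 24 to 34 hours after it, in patients who took every dose.

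**The case against.** **Stoppers may never reach the Day 5 tables.** Day 5 sampling times are defined by a morning dose that these patients did not take, and the sufficient-data condition could be read as excluding them. This stands in part: a reader might infer that off-drug samples certainly enter the steady-state parameters, and the documents do not establish that. But exclusion would then rest on an analyst's reading, against an estimand that says to include.

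**Day 7.** A reader might also infer that Day 7 concentrations understate exposure on the regimen. They do not measure it. Day 7 follows the last scheduled dose for every patient, so early stoppers only alter a washout mean. What remains is that the footnote times the sample from a tenth dose that they did not take.

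**The population model already copes.** This stands. SAP 5.7.3 fits dose, concentration and time data for AT-511 and AT-273, so stopped dosing can be represented. The problem is confined to descriptive summaries.

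**The size is speculative and the known facts point low.** No one stopped among 10 actively treated healthy volunteers (Protocol 1.2) or 10 HCV patients treated for 8 to 12 weeks (Protocol 5.1.1). That is fair, but with 0 of 20 the one-sided 95% upper limit is 1 − 0.05^(1/20) = 13.9%, so the assumed range is not ruled out. Zero residual drug for all four analytes is the worst case, which is why r = 0.5 is shown as well.

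**Placebo means.** The mean-for-each-treatment cell is marked as continued and matches the vital-sign and laboratory rows above it. Since Protocol 4.2.2 leaves placebo samples unassayed except by request, nobody is likely to produce placebo means. This is a wording matter only.

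**Conclusion.** The point holds as a low-severity inconsistency. Table 2 states a rule for stopping drug that is wrong for a steady-state summary, and nothing elsewhere overrides it. If off-drug samples are analysed as the rule says, the Day 5 arithmetic means fall by at most the share off drug: 1% to 10% over the assumed range, and half that if stoppers keep half the on-drug concentration. The geometric mean is more fragile, since one value set to zero is enough to break it. Medians shift less than the worst-case mean, and the population model is little affected.

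The size rests on an assumed discontinuation rate, on assumed residual concentrations, and on stoppers attending and being sampled. The point does not extend to a biased Day 7 measure of exposure, to the population PK results, or to the primary test, its significance level or the sample size.

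**What to change.** In the SAP:

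1. In the PK row of Table 2, replace treatment policy with an on-treatment rule for treatment withdrawal.
2. Restrict the Day 5 by-timepoint summaries and Cmax,ss, Tmax,ss and Ctrough,ss to samples whose preceding scheduled doses are documented on the Study Drug Administration eCRF. Fix before unblinding how many doses this means; all doses due up to the sample is the simplest choice.
3. List the excluded samples and keep them in the population PK model.
4. Present Day 7 as a post-treatment sample, by actual time since the last dose taken.
5. State that the PK summaries are for the AT-527 arm only.

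It would also help to say how zeros enter geometric means and geometric CVs, because values below the limit can occur in patients on drug too.

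The cost is a few lines of SAP text and a flag built from dose and timing data that Protocol 4.3.2 already has sites record. The downside is slightly fewer samples in the descriptive tables.
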